The Adverse Events (AEs) observed to date in Phase I and Phase II trials are consistent with those reported for other EGFR tyrosine kinase inhibitors (dose dependent diarrhea and skin-related adverse events including rash and acne). Other AEs were in the expected range for patients with advanced cancer disease (ref investigator's brochure). In the BIBW 2992 Phase I monotherapy trials, the most frequent drug-related adverse events were associated with gastrointestinal disorders (diarrhea, nausea, vomiting, stomatitis), skin and subcutaneous tissue disorders (rash, dry skin, pruritus, acneiform rash, and acne), general disorders and administration site conditions (fatigue, mucosal inflammation), respiratory disorders (epistaxis, typically grade 1), and metabolism and nutritional disorders (anorexia, dehydration).

Diarrhea is the single most often reported gastrointestinal AE. An increased incidence of diarrhea grade 3 has been observed in phase II monotherapy trials (starting dose of 50 mg qd). Prompt and proactive management of diarrhea together with timely treatment pause and dose reduction is crucial to reduce the severity of diarrhea and its potential complications such as dehydration leading to serum electrolyte changes (hyponatraemia, hypokalaemia and hypomagnesaemia) and/or renal impairment.

Nausea and vomiting are the other commonly reported gastrointestinal adverse events and can be generally managed successfully with the use of antiemetics.

Skin related adverse events present in a number of forms, i.e., rash (including erythematous, maculopapular, papular, etc.), acne, dermatitis acneiform, dry skin, skin reaction and pruritis. Folliculitis as well as nail changes (including paronychia) are other reported manifestations of skin-related adverse events with BIBW 2992. Early and adequate management of skin-related adverse events can reduce the frequency and the severity of them.

Further AEs included oral discomfort (stomatitis, mouth ulceration, oral pain, dry mouth, soft tissue disorder) and mucosal inflammation. Conjunctivitis and rhinorrhea as a result of inflammation in the mucosal membranes have been reported. Mucosal and skin dryness can lead to epistaxis, which has to date been observed at CTCAE Grade 1. Anorexia, fatigue and asthenia are also frequently observed.

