Of 22 evaluable patients with NSCLC from Phase I trials with BIBW 2992, there have been four partial responses (PRs) (3 confirmed and 1 unconfirmed PR) ranging in duration from 5 months to 24 months. All 4 patients were non-smoking Caucasian with adenocarcinoma of the lung. In two of these three patients with confirmed PR, EGFR sequencing has shown exon 19 in-frame deletions.

The efficacy and safety of BIBW 2992 in NSCLC patients with EGFR mutations is under evaluation in a phase II trial (LUX-Lung 2). In this trial, patients with Stage IIIB/IV lung adenocarcinoma with

EGFR mutation in exons 18-21 and failure of one line of systemic chemotherapy were treated with BIBW 2992 at a dose of 50 mg once daily until disease progression. The trial underwent two major amendments. The first was to decrease the starting dose to 40 mg once daily and the second was to allow inclusion of chemotherapy-naïve patients. 129 patients were enrolled. Preliminary results were presented in August 2009 at the World Congress on Lung Cancer. The response rate was 63% in the first-line patients and 66% in the second-line patients. Diarrhea and skin-related adverse events have been the main side effects but have been manageable with appropriate dose interruption/reduction. The incidence of grade 3 diarrhea was lower at 40 mg (4.3%) than at 50 mg (30%). Survival data are not yet mature for analysis.

A global, randomized, phase III trial (LUX-Lung 3) is currently ongoing and is assessing the progression-free survival difference between first-line BIBW 2992 and first-line chemotherapy with cisplatin and pemetrexed in NSCLC patients with EGFR mutations.

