#### **4.4 Registration Process for Other Participating Institutions**

CONFIDENTIAL

This document is confidential. Do not disclose or use except as authorized.

To register a participant, the following documents should be completed by the Participating Institution and faxed or e-mailed to the Lead Institution at the following address:

[REDACTED]

- Progress note confirming performance status, lack of prior EGFR TKI, absence of CNS metastases or confirmation of the treatment and stability of known CNS metastases, absence of another malignancy within 3 years, and detailing other significant past medical history
- Copy of required laboratory, pathology, and radiology tests including:
  - Pathology report confirming NSCLC and EGFR mutation status
  - Radiology report confirming measurable or evaluable disease and cardiac ejection fraction  $\geq 50\%$
  - Laboratory tests including CBC with differential, creatinine, ALT, AST, and bilirubin
  - An ECG, reviewed, signed and dated by MD listed on 1572
- Signed informed consent form. Only MDs listed on the 1572 can sign consent for the study.
- HIPAA authorization form (if separate from the informed consent document)
- Other appropriate forms (e.g., Eligibility Screening Worksheet, Registration form). The eligibility worksheet must be signed by the MD confirming the eligibility of the patient. Registrations cannot be processed without appropriate signature.

The research DF/HCC Multi-center Protocol Participating Institution will then call or e-mail the Lead Institution or designee to verify eligibility. To complete the registration process, the Lead Institution or designee will:

- Register the participant on the study with the DF/HCC Quality Assurance Office for Clinical Trials (QACT)
- Fax or e-mail the participant case number, and if applicable the dose treatment level, to the Participating Institution
- Call the research nurse or data manager at the Participating Institution and verbally confirm registration

Randomization can only occur during QACT's normal business hours of 8:00 am to 5:00 PM Eastern Time.

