### **5.9.1 Suggested Management of Diarrhea**

Close monitoring and proactive management of diarrhea is essential for successful treatment of patients with BIBW 2992. Early and appropriate intervention can prevent the development of more severe diarrhea. In most cases, loperamide (Imodium) controls diarrhea caused by BIBW 2992.

The recommendations for management are as follows:

- If any diarrhea is experienced (CTCAE Grade 1), two 2 mg loperamide tablets (total dose 4 mg) should be taken immediately, followed by one 2 mg tablet with every loose bowel movement, up to a maximum daily dose of 8 tablets (16 mg).
- Other anti-diarrheal medications that could be used include: Lomotil (5 mg, four times a day), or tincture of opium (15-20 drops orally every 4 hours) or octreotide (150 to 300  $\mu$ g SQ twice a day).
- Oral hydration is important regardless of severity of diarrhea; appropriate rehydration (1.5 L/m^2/day plus equivalent of actual fluid loss) and electrolyte replacement should be recommended in the event of CTCAE Grade 2 and Grade 3 diarrhea.

CONFIDENTIAL

This document is confidential. Do not disclose or use except as authorized.

- For CTCAE Grade 3 diarrhea or CTCAE Grade 2 diarrhea lasting  $\geq$  2 days (48 hours) despite adequate antidiarrheal treatment, BIBW 2992 must be held until recovery to CTCAE  $\leq$  Grade 1. Upon recovery, BIBW 2992 should be resumed at a reduced dose according to the dose reduction scheme outlined in Section 5.5
- If despite optimal supportive care and a treatment pause, diarrhea does not resolve to CTC Grade  $\leq$  1 within 28 days, the patient should be removed from protocol therapy.

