### **6.1.3 Laboratory Examinations**

Laboratory examinations to be performed during screening include hemoglobin, white blood cell count including neutrophil count (sum of polysegmented granulocytes and band forms), platelets, bilirubin, alkaline phosphatase, ALT, AST, blood urea nitrogen (BUN), creatinine, calcium, electrolytes (sodium, potassium), and a urine pregnancy test (for women of child-bearing age).

Laboratory examinations are to be performed at the start of each cycle of treatment, on days 8 and 15 of cycle 1, and at the time of study discontinuation include hemoglobin, white blood cell count including neutrophil count (sum of polysegmented granulocytes and band forms), platelets, bilirubin, alkaline phosphatase, ALT, AST, blood urea nitrogen (BUN), creatinine, calcium and electrolytes (sodium, potassium).

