## 9. STUDY CALENDAR

Screening evaluations are to be conducted within 4 weeks prior to start of protocol therapy, unless otherwise noted. All assessments must be performed prior to administration of any study medication. All study assessments and medications should be administered within  $\pm$  3 days of the protocol-specified date, unless otherwise noted.

	Screening	Treatment Period ( $\pm$ 3 days)											Off-Study a	Survival Follow-up
Cycleb (C) and Day (D)	Day-28 to 0	C1 D1	C1 D8	C1 D1 5	C2 D1	C3 D1	C4 D1	C5 D1	C6 D1	C7 D1	C8+			
Informed consent and confirmation of eligibility	X													
Medical History, Vitals, Physical Exam and AEs c	X	X	X	X	X	X	X	X	X	X	X d	X		
Concomitant medications	X	X	X	X	X	X	X	X	X	X	X d	X		
Laboratory testing e	X	X	X	X	X	X	X	X	X	X	X d	X		
ECG	X													
Tumor assessment (RECIST) g	X					X		X			X	X g	X	
Circulating Tumor Cell (CTC) Assay h		X	X	X	X	X	X	X		X	X h	X		
Repeat Tumor Biopsy i												X		X i
Survival and subsequent therapy j														X

- a Off-Study visit** – The off-study assessments will be performed when the subject meets criteria for study discontinuation (see Section 5.10).
- b Cycles** are 28 days long
- c Vitals** include temperature, blood pressure, respiratory rate, pulse, height, weight, performance status. **Medical history** should include recording all interim illnesses and assessment of **adverse events**.
- d After Completion of Cycle 8** visits for medical history, vitals, physical exam, assessment of adverse events, concomitant medications and laboratory evaluations need only be done every 2 months. These visits will correspond with the schedule for restaging scans (see below) and can be thought of as occurring after cycles 8, 10, 12, etc or can also be thought of as occurring at the beginning of cycles 9, 11, 13, etc.

test (if applicable). Studies to be done at the start of each cycle of treatment include CBC, LFTs, BUN, Cr, calcium, and electrolytes.

- f Tumor Measurement** – Baseline scans can be performed up to 28 days prior to start of treatment. Follow-up scans should be performed within 10 days of the start of cycles 3, 5, 7, 9, etc. This can also be thought of as following cycles 2, 4, 6, 8, etc.

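### Low magnesium is named as a complication of diarrhea on BIBW 2992, but no baseline or scheduled magnesium is planned, so asymptomatic cases may be missed or found unevenly across sites

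*Combined protocol and SAP*

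**What the plan says.** Section 2.1.3 describes diarrhea as the most common gastrointestinal adverse event on the drug and gives its possible consequences as "dehydration leading to serum electrolyte changes (hyponatraemia, hypokalaemia and hypomagnesaemia) and/or renal impairment".

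Section 6.1.3 sets out the laboratory tests. The screening list includes "creatinine, calcium, electrolytes (sodium, potassium), and a urine pregnancy test". The list for cycle starts, days 8 and 15 of cycle 1, and discontinuation ends with "creatinine, calcium and electrolytes (sodium, potassium". Calcium is listed separately in both; magnesium is in neither.

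The readable part of the laboratory footnote in section 9 says: "Studies to be done at the start of each cycle of treatment include CBC, LFTs, BUN, Cr, calcium, and electrolytes". It does not define electrolytes, and its opening is lost in the extracted text. After cycle 8, "laboratory evaluations need only be done every 2 months".

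Section 4.4 asks other institutions for "Laboratory tests including CBC with differential, creatinine, ALT, AST, and bilirubin" at registration.

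On management, section 5.9.1 says "electrolyte replacement should be recommended in the event of CTCAE Grade 2 and Grade 3 diarrhea". It ties no electrolyte measurement to a diarrhea episode.

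Section 6.2.1 treats an abnormal laboratory value as an adverse event only when it produces signs or symptoms, or calls for treatment or further testing.

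**The concern.** The protocol names three electrolyte disturbances as consequences of the drug's leading gastrointestinal toxicity, then schedules tests for two of them. It gives no reason for leaving out the third.

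Symptomatic or treated low magnesium remains reportable under sections 6.2.1 and 6.3. The gap is the asymptomatic low value that would have prompted treatment or further tests had anyone seen it. With no planned measurement, finding it depends on local ordering in a multi-center study.

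A value taken on treatment also has nothing to be compared with. This matters because section 5.8.2 requires toxicities that delayed treatment to return to grade 1 or baseline, and the notes to Table 2 define baseline as the grade at the start of treatment.

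The stakes are limited to completeness of safety data. The only safety objective in section 1.3 concerns repeat biopsies, and section 12.6 is a descriptive summary.

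**Working it through.** The plan states no figure on this point, so there is none to reproduce. The check has four parts.

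**1. Named risks against scheduled tests**

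| Complication named in 2.1.3 | Screening list, 6.1.3 | On-treatment list, 6.1.3 |
|---|---|---|
| Low sodium | sodium | sodium |
| Low potassium | potassium | potassium |
| Low magnesium | none | none |
| Renal impairment | BUN, creatinine | BUN, creatinine |

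The finding rests on 6.1.3, which is complete. The calendar footnote is partly lost. The registration list in 4.4 omits sodium and potassium as well, so its silence on magnesium adds little.

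**2. Scheduled panels per patient**

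Inputs: about 10 months on therapy (12.1), taken as 304 days; 28-day cycles; the calendar in section 9.

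- Screening, C1D1, C1D8, C1D15: 4
- C2D1 to C8D1 (days 29 to 197): 7
- Every second cycle after that, C9D1 (day 225) and C11D1 (day 281): 2
- Off-study visit: 1

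Total: 4 + 7 + 2 + 1 = 14. For the 24 patients in 12.1, 14 × 24 = 336. For the 20 in 1.1, 14 × 20 = 280.

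**3. Patients with the risk factor**

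Section 2.1.3 gives grade 3 diarrhea rates from an earlier phase II trial of 4.3% at 40 mg and 30% at 50 mg.

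- 24 patients: 24 × 0.043 = 1.03; 24 × 0.30 = 7.2
- 20 patients: 20 × 0.043 = 0.86; 20 × 0.30 = 6.0

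The upper figures apply the 50 mg rate to everyone, which section 5.4 excludes: all patients start at 40 mg, and any diarrhea in cycle 1 bars escalation. The low end fits better. These are counts of patients with severe diarrhea, not with low magnesium.

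**4. Chance that a scheduled draw falls inside an episode**

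For an episode of L days starting at a random time, with L no longer than the gap between draws, the chance is L / gap. The documents give no episode length; I assume 2 to 7 days.

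| Period | Gap (days) | L = 2 | L = 7 |
|---|---|---|---|
| Cycle 1, days 1 to 15 | 7 | 2/7 = 29% | 7/7 = 100% |
| Day 15 to C2D1 | 14 | 2/14 = 14% | 7/14 = 50% |
| Cycles 2 to 8 | 28 | 2/28 = 7% | 7/28 = 25% |
| From cycle 9 | 56 | 2/56 = 4% | 7/56 = 12.5% |

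These chances are the same for sodium, potassium and magnesium. A scheduled magnesium would give a baseline, fair cover in the first two weeks, and after cycle 1 mainly a periodic check.

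**The case against.** The strongest reply is that the protocol controls this risk through management rather than testing. Section 5.9.1 starts loperamide at grade 1, recommends rehydration and electrolyte replacement at grades 2 and 3, and requires the drug to be held at grade 3, or at grade 2 lasting 48 hours despite treatment, and then resumed at a reduced dose. Nothing stops a site from measuring magnesium, and no rule requires every named complication to have its own scheduled assay. Adding magnesium to the routine panel also does little for an acute episode after cycle 1. Finally, no document describes differences between sites in magnesium testing, and in a single-arm pilot uneven ascertainment biases no comparison between arms.

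Much of this stands. It limits the point to a small gap in safety data, and the unevenness across sites is an inference. But prompt management does not supply a baseline, and discretionary testing is exactly what would make detection uneven. The limited acute cover applies equally to sodium and potassium, which the protocol nevertheless schedules.

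**Conclusion.** The omission is certain on the text: of the three electrolyte complications the protocol names, only magnesium has no baseline or scheduled value, and none of the 14 panels per patient includes it as 6.1.3 defines them.

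The consequence is plausible but cannot be sized. It is confined to asymptomatic low values that would have needed treatment or further tests. The documents give no rate of hypomagnesaemia, and the amount of unscheduled testing is unknown. The nearest figure is about 1 patient in 24 with grade 3 diarrhea at the 40 mg rate, with 7 as a ceiling that the dosing rules make unrealistic.

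The panel count assumes 304 days on therapy, and the draw-overlap figures assume episodes of 2 to 7 days. The T790M endpoint, sample size, significance level and power are untouched. This is a minor, inexpensive improvement worth considering.

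**What to change.** In both paragraphs of section 6.1.3, add magnesium to the bracketed list of electrolytes, and name it in the laboratory footnote of section 9.

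Optionally, in section 5.9.1 recommend measuring sodium, potassium and magnesium together whenever grade 2 or higher diarrhea calls for electrolyte replacement. This is the step that would cover an acute episode, and all three electrolytes lack it now.

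The panel change costs about 14 assays per patient (336 in 24 patients, 280 in 20) on blood already drawn, plus one case report form field. The optional check may need an occasional unscheduled draw: for grade 3 diarrhea probably in about 1 of 24 patients, and at most about 7, plus grade 2 episodes, whose rate the documents do not give.

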## **2.2 Study Disease**

### **2.2.1 Non-Small Cell Lung Cancer, EGFR Mutations, and Tyrosine Kinase Inhibitors**

Non-small cell lung cancer (NSCLC) is the most common cause of cancer mortality in men and women in the U.S. Approximately 170,000 Americans will be diagnosed with NSCLC this year and approximately half of them will have advanced or metastatic disease at presentation, which is not curable. Chemotherapy and biologically targeted agents can extend survival modestly for these patients; however, discovery of novel ways to prolong the disease course is a top research priority.

The epidermal growth factor receptor (EGFR) signaling pathway plays a central role in the neoplastic transformation of NSCLC and promotes cancer cell survival, metastasis, and angiogenesis. The predominance of EGFR signaling in NSCLC makes the pathway an attractive candidate for the development of targeted therapeutics. In the last six years, the FDA has approved two drugs in this class for salvage treatment of NSCLC, gefitinib (Iressa ®, formerly known as ZD1839) and erlotinib (Tarceva ®, formerly known as OSI-774). Both are small molecule orally-bioavailable tyrosine kinase inhibitors (TKIs) of the EGFR TK domain. Erlotinib improves survival compared to placebo when administered after failure of first line or second line chemotherapy for advanced NSCLC and is currently approved for that indication. Gefitinib received accelerated approval for salvage treatment of NSCLC based on response to treatment and symptom improvement in phase II clinical trials. A randomized placebo-controlled trial failed to demonstrate a survival benefit and gefitinib is now only available in the US if participating in a clinical trial, though it is widely used elsewhere in the world.

Our group and others described somatic mutations in the *EGFR* gene that sensitize NSCLC tumors to TKIs, present in about 10% of unselected US patients with NSCLC but in up to 50% of never-smoking NSCLC patients. Activating EGFR mutations primarily consist of overlapping deletion mutations in the LREA region of exon 19 or the point substitution mutation L858R in exon 21, though there are several other rare activating mutations described in the literature. EGFR mutations confer a state of “oncogene addiction” on the molecular biology of the tumor, such that the critical downstream signaling pathways are solely controlled by EGFR and are therefore highly susceptible to cell death by blockade of EGFR. Our group has previously demonstrated that patients with advanced NSCLC and EGFR mutations treated with first-line gefitinib have a median progression free survival of 9.2 months, and median overall survival of 17.5 months. This study is consistent with other trials using EGFR-TKI treatment in patients with mutations, which demonstrate response rates >50% and time to progression of >9 months

CONFIDENTIAL

This document is confidential. Do not disclose or use except as authorized.

Such a “genotype-directed” treatment strategy has now been proven effective in 2 randomized trials. The IPASS study was conducted in Asia where EGFR mutation incidence is higher. All patients were non-smokers or former light smokers (quit at least 15 years prior and  $\leq$  10 pack years history) and all had newly-diagnosed advanced adenocarcinoma. Patients were randomly assigned to front-line gefitinib or front-line chemotherapy with carboplatin and paclitaxel. The study utilized a non-inferiority design powered to demonstrate that the 95% confidence interval (CI) for the hazard ratio (HR) for PFS of gefitinib compared to chemotherapy lay entirely below the target of 1.2. The overall PFS HR was 0.74 (95% CI 0.65-0.85), showing that gefitinib was not only non-inferior, but was actually superior to chemotherapy. Even more illustrative was the molecular sub-group analysis. EGFR mutation status was available for 36% of patients and the mutation-positive rate was 60% in this clinically-enriched study. For mutation-positive patients the results favored gefitinib even more strongly, with a PFS HR of 0.48 (95% CI 0.36-0.64). Conversely, for mutation-negative patients, chemotherapy was a better treatment with a PFS HR of 2.95 (95% CI 2.05-3.98). In other words, for patients known to harbor an EGFR mutation, gefitinib was more effective than carboplatin and paclitaxel with regards to PFS, but for patients who fit the “clinical phenotype” of a TKI-responder, the genotype trumped the phenotype and TKI therapy did not have a good outcome. This landmark study argues that patients with a moderate chance of harboring an EGFR mutation should undergo molecular testing at the time of diagnosis, and if an EGFR mutation is identified, therapy with an EGFR TKI should be strongly considered.

The other recent randomized study regarding a genotype-directed treatment strategy was published in abstract form only thus far and is a smaller study, but all patients enrolled were positive for an EGFR mutation so the molecular results are not a subgroup analysis but the entire study cohort. This trial consisted of Japanese patients with newly diagnosed advanced adenocarcinoma with EGFR mutations randomized to front-line gefitinib or front-line chemotherapy with carboplatin and paclitaxel. The primary end-point was again PFS and the study was powered for 320 patients and an anticipated HR of 0.69, favoring gefitinib. An interim analysis after 200 patients demonstrated a benefit for gefitinib with HR 0.36 (95% CI 0.25-0.51).

In sum, these studies suggest that patients harboring an EGFR mutation derive significant clinical benefit from treatment with EGFR-TKIs. As a result, EGFR TKI therapy is the emerging standard of care treatment for this population, including as front line therapy. The European Union’s medicine administration recently granted approval of gefitinib specifically for patients harboring an EGFR mutation and several oncology care guidelines in the US are being modified to include EGFR mutation screening and consideration of an EGFR TKI for these patients.

